2.9 Pharmacokinetic endpoints

PK trough sampling will be performed in all subjects at visit 299.

[figure not shown]
Plasma concentration of LIK066 will be summarized by treatment. Descriptive statistics includes n, mean, standard deviation, minimum, median, maximum, coefficient of variation (%) for arithmetic mean, geometric mean, and coefficient of variation (%) for geometric mean.

[figure not shown]
[figure not shown]
Concentrations below the lower limit of quantification (LLOQ) will be treated as zero in summary statistics. A geometric mean will not be reported if the dataset includes zero values.

Individual LIK066 plasma concentration data will be listed by treatment, subject, and visit.

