5.5.4 Instructions for prescribing and taking study treatment

All kits of study treatment assigned by the NIRT will be recorded/databased in the NIRT.

The investigator should ensure that the subject clearly understands the dosing instructions outlined below.

- At Visit 101 (Epoch 2), each subject will be dispensed study drug containing blisters with study medication. The blisters are constructed to easily deliver the daily required number of tablets for the morning dose. The kits contain sufficient medication for the run-in period of up to 4 weeks until Visit 199/201.
- From Visit 201 till Visit 299 (Epoch 3), subjects will be dispensed study drug containing blisters with study medication. The blisters are constructed to easily deliver the daily required number of tablets for the morning dose. The kits contain sufficient medication for the time between each visit according to [Table 6-1](#).

In Epoch 2 and Epoch 3, subjects will be instructed to take 1 tablet LIK066 (or matching placebo) in the morning, immediately before the meal. Study drug should be taken the same time throughout the study.

No study drug should be taken on the morning of a study visit; subjects with T2DM should not take their anti-diabetic treatment. Subjects should arrive in the fasting state; ie no food or drinks (except water) for a minimum of 8h before the scheduled visit. If the subject has not fasted for an adequate period of time, the collection of fasting laboratory evaluations must be rescheduled. The study drug regimen (and, if applicable, rescue medication as defined in [Section 5.5.6](#)) should not be taken prior to obtaining the fasting laboratory test samples.

If a dose is missed and the subject realizes this within 4h, the study drugs should be taken otherwise the subject should take the next scheduled dose.

Previously dispensed study medication blisters, including any remaining study medication, must be returned to the study center at each study visit.

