5.6.2 Discontinuation of study treatment

Discontinuation of study treatment for a patient occurs when study drug is stopped earlier than the protocol planned duration, and can be initiated by either the patient or the investigator or the sponsor (see [Section 5.6.5](#)).

The investigator must discontinue study treatment for a given patient if, on balance, he/she believes that continuation would negatively impact the risk/benefit of trial participation.

Study treatment must be discontinued under the following circumstances:

- Patient wish
- Pregnancy (see [Section 6.5.5](#) and [Section 7.6](#))
- Use of prohibited treatment (see [Section 5.5.8](#))
- Any situation in which study participation might result in a safety risk to the patient
- Emergence of the following AE: ketoacidosis (see also [Section 7.8.1](#)), or lower limb amputation (including toe amputation)
- Any laboratory abnormalities that in the judgment of the investigator, taking into consideration the subject's overall status, prevents the subject from continuing participation in the study.
- Subjects whose study treatment has been unmasked (see [Section 5.5.9](#))
- Withdrawal of consent (see [Section 5.6.3](#))

If discontinuation of study treatment occurs, the patient should NOT be considered withdrawn from the study. The patient should return to the study site as soon as possible, after discontinuation of study drug, for a study treatment discontinuation visit. Treatment discontinuation visit assessments detailed in the “unscheduled treatment discontinuation visit” (UNS) in [Table 6-1](#) should be completed and recorded in the eCRF. The investigator must determine the primary reason for the patient's premature discontinuation of study treatment and record this information on the Dosage Administration eCRF.

After study treatment discontinuation, at a minimum, in abbreviated visits, the following data should to be collected at clinic visits or via telephone visits:

- new and/or concomitant treatments
- adverse events/Serious Adverse Events

If the patient cannot or is unwilling to attend any visit(s), the site staff should attempt telephone contact with the patient, or with a person pre-designated by the patient. This telephone contact should preferably be done according to the study visit schedule.

The investigator must also contact the NIRT to register the patient's discontinuation from study treatment.

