5.6.5 Early study termination by the sponsor

The study can be terminated by Novartis at any time for any reason. This may include reasons related to the benefit risk assessment of participating in the study, practical reasons, or for regulatory or medical reasons (including slow enrolment). Should this be necessary, the patient must be seen as soon as possible and treated as a prematurely withdrawn patient. The investigator may be informed of additional procedures to be followed in order to ensure that adequate consideration is given to the protection of the patient's interests. The investigator will be responsible for informing the Institutional Review Board/Independent Ethics Committee (IRBs/IECs) of the early termination of the trial.

6 Visit schedule and assessments

[Table 6-1](#) lists all of the assessments and indicates with an “x” when the visits are performed.

Subjects must be seen for all visits on the designated day, or as close to it as possible. Missed or rescheduled visits should not lead to automatic discontinuation. Patients who prematurely discontinue the study for any reason should be scheduled for a visit as soon as possible, at which time all of the assessments listed for the final visit will be performed. At this final visit, all dispensed investigational product should be reconciled and the adverse event and concomitant medications reconciled on the CRF.

Subjects will be contacted for safety evaluations during the 30 days following the last administration of study treatment.

Table 6-1 Assessment schedule

Epoch	1 Screening	2 Run-in			3 Treatment				
Visit	1	101	102	199	201 RND	202	203	204	299* TD/ PSD/EOS
Week	-6	-4	-2 - -1	0		2	4	8	12
Screening assessments									
Informed consent	X								
Inclusion/exclusion (Section 4)	X			X	X				
Subject demographics (Section 6.2)	X								
Medical history	X								
Medical history: protocol solicited events	X								
Smoking & alcohol history (Section 6.2)	X								
Efficacy									
Height (Section 6.4.1)	X								
Weight (Section 6.4.1)	X	X		X	X	X	X	X	X
Waist circumference (Section 6.4.2)	X	X			X	X	X	X	X
BP (SBP & DBP) (Section 6.4.5)	X	X			X	X	X	X	X
HbA1c (Section 6.4.3)	X				X				X
FPG (Section 6.4.4)	X				X				X
Fasting lipid profile (Section 6.4.6)	X [†]				X				X
hsCRP (Section 6.4.6)					X				X
Uric acid (Section 6.4.7)					X				X
Urine albumin and Urine albumin to creatinine ratio (Section 6.4.8)					X				X
VFA and SFA by CT (Section 6.4.9)			X [†]						X

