Epoch	1 Screening	2 Run-in			3 Treatment				
Visit	1	101	102	199	201 RND	202	203	204	299* TD/ PSD/EOS
Week	-6	-4	-2 - -1	0		2	4	8	12
Safety									
Complete physical exam (Section 6.5.1)	S								S
Short physical exam (Section 6.5.1)		S		S	S	S	S	S	
Vital signs (Section 6.5.2)	X	X			X	X	X	X	X
Hematology (Section 6.5.3.1)	X				X		X		X
Biochemistry (Section 6.5.3.2)	X				X		X		X
TSH (Section 6.5.3.2)	X								
Pregnancy test (serum, Section 6.5.5)	X								
Pregnancy (urine dipstick, Section 6.5.5)				X	X				X
Hematuria (urine dipstick, Section 6.5.3.3)	X								
Urinalysis (Section 6.5.3.3)					X				X
PK trough (Section 6.6.3)									X
ECG (Section 6.5.4)	X								X
AEs (Section 7.1)		X		X	X	X	X	X	X
SAEs (Section 7.2)		X		X	X	X	X	X	X
Ketoacidosis AEs (Section 7.8.1)		X		X	X	X	X	X	X
Hypoglycemia AEs (Section 7.8.2)		X		X	X	X	X	X	X

Epoch	1 Screening	2 Run-in			3 Treatment				
Visit	1	101	102	199	201 RND	202	203	204	299* TD/ PSD/EOS
Week	-6	-4	-2 - -1	0		2	4	8	12
Medication records									
Prior & concomitant medications	X	X		X	X	X	X	X	X
Surgical and medical procedures		X		X	X	X	X	X	X
Dose administration record		X		X	X	X	X	X	X
Administrative procedures									
NIRT system	X	X		X	X	X	X	X	X
Lifestyle instructions (Section 3.1.1)		S			S	S	S	S	
Dispense glucometer (T2DM subjects)		S							
Glycemia diary (T2DM subjects)				S	S	S	S	S	S
Study drug accountability				S	S	S	S	S	S
Screening phase disposition	X								
Run-in phase disposition				X					
Study completion									X

TD = Study treatment discontinuation; PSD = Premature subject discontinuation; X = assessment to be recorded on clinical data base; S = assessment to be recorded on source documentation only; RND = Randomization visit; EOS = end of study; * These assessments are also to be conducted for subjects who prematurely withdraw from the study; † -14 ~ -8 days; ‡ TG only

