9.5.4 Pharmacokinetics

Individual LIK066 plasma concentration data will be listed by treatment, subject, and visit. Concentrations below the lower limit of quantification will be treated as zero in summary statistics. A geometric mean will not be reported if the dataset includes zero values.

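### SAP 2.9 sets no condition on time since last dose, so wash-out samples from early-stop visits can enter the Visit 299 trough summary

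*SAP*

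**What the plan says.** Pharmacokinetics is a stated secondary objective, and trough concentration is its only listed endpoint (Protocol Table 2-1, SAP Table 1-1). SAP 2.9 plans one sample per patient: "PK trough sampling will be performed in all subjects at visit 299". A scheduled sample is a trough because of Protocol 5.5.4: "No study drug should be taken on the morning of a study visit".

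In Protocol Table 6-1 the only PK mark is in the Visit 299 column, which is also headed TD, PSD and EOS (treatment discontinuation, premature subject discontinuation, end of study). Its footnote adds: "These assessments are also to be conducted for subjects who prematurely withdraw from the study". Protocol 5.6.2 sets the timing after stopping drug: "The patient should return to the study site as soon as possible, after discontinuation of study drug, for a study treatment discontinuation visit". Protocol section 6 says the same for leaving the study: "Patients who prematurely discontinue the study for any reason should be scheduled for a visit as soon as possible", with all final-visit assessments. Neither text gives a maximum interval.

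SAP 2.9 then summarises plasma concentration by treatment. Protocol 9.5.4 sets the rule for low values: "Concentrations below the lower limit of quantification will be treated as zero in summary statistics". SAP 2.9 has the same rule and continues: "A geometric mean will not be reported if the dataset includes zero values".

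**The concern.** A trough in a once-daily regimen is the concentration one dosing interval after the last dose. A patient who stopped drug and returns several days later gives a wash-out concentration instead. The visible text of SAP 2.9 does not separate the two. SAP 2.2 defines no PK analysis set, and the 7-day on-treatment rule in SAP 2.5.4 applies to body weight only. A patient whose drug is interrupted for safety at Week 12, which Protocol 5.5.5 allows, raises the same problem.

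What is at stake is the meaning of the trough table. Each arm's figures could depend partly on how many patients stopped early and how late they came back. The planned listing is by treatment, subject and visit, so it would not by itself show which values are off-drug.

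**Working it through.** The PK plan states no figure, so there is nothing to reproduce. The power in Protocol Table 9-1 concerns body weight and uses no PK data.

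**Inputs from the documents.** Arm sizes are about 20 (2.5 mg and 10 mg) and about 30 (25 mg and 50 mg), from Protocol 5.2. The four active arms together have 20 + 20 + 30 + 30 = 100 patients.

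**Inputs that must be assumed.** Let d be the share of patients who stop early. Let q be the share of those whose sample is taken and is below LLOQ. The documents give neither.

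**Chance of losing a geometric mean.** Read the undefined word dataset in the geometric-mean rule as one arm. With p = d × q, the chance of at least one zero in an arm of n is 1 − (1 − p)^n. The chance that all four active arms keep a geometric mean is (1 − p)^100.

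| d | q | p | n = 20 | n = 30 | All four active arms keep it |
|---|---|---|---|---|---|
| 2% | 0.25 | 0.5% | 9.5% | 14.0% | 60.6% |
| 5% | 0.25 | 1.25% | 22.2% | 31.4% | 28.4% |
| 5% | 0.5 | 2.5% | 39.7% | 53.2% | 8.0% |
| 10% | 0.5 | 5% | 64.2% | 78.5% | 0.6% |

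For example, 1 − 0.9875^20 = 0.222 and 1 − 0.9875^30 = 0.314.

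**Effect on the averages.** A share s of zeros multiplies the arithmetic mean by 1 − s. One zero in 20 gives 0.95, and a 10% share gives 0.90. If wash-out values stay quantifiable at a fraction f of the true trough, the geometric mean is multiplied by f^s. With s = 10%, f = 0.5, 0.1 and 0.01 give 0.93, 0.79 and 0.63.

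**After the fix.** Early-stop samples taken more than one dosing interval after the last dose would add no zeros. A geometric mean could then be lost only through a true trough below LLOQ. That chance cannot be computed from the documents.

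**The case against.** The strongest reply is that the harm depends on a chain of events. A patient must stop early, attend, be sampled well past one dosing interval and, for the geometric mean to go, be below LLOQ. A visit on the morning after the last dose still yields a trough. Patients who withdraw consent as Protocol 5.6.3 defines it do not allow analysis of samples already taken, so they need not contribute. All of this stands, and it is why the size is only an illustration.

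The 10% in the sample-size section is not evidence for d. It is a power allowance for losses to follow-up, and a patient lost to follow-up gives no sample. The last row of the table is therefore a high illustrative value and not the plan's expectation.

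The labelling of visits is also unclear. Protocol 5.6.2 calls the stopping visit an unscheduled one and refers to Table 6-1, but the table as reproduced shows only the shared Visit 299 column. SAP 1.1.2 equates Visit 299 with Week 12. Early-stop samples might carry another label and stay out of the summary, but nothing visible says so. Sampling details are in a laboratory manual that is not among the documents, and SAP 2.9 has gaps where figures are not shown.

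A reader might infer that the PK objective will be answered with non-trough data or with no usable average. The documents do not support that. Completers' Week 12 samples are drawn with the morning dose held. The n, arithmetic mean, SD, median, minimum, maximum and arithmetic CV are reported in any case, and individual values are listed. A reader might also infer that Phase 3 dose selection would be distorted. Protocol 9.4.2 bases target dose selection on modelled weight loss, SAP 2.10 marks PD and PK/PD analyses as not applicable, and no figure suggests that stopping rises with dose.

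**Conclusion.** The gap is real but limited. As written, the plan allows off-drug concentrations into a table meant to report trough, and one such value below LLOQ is enough to remove a geometric mean. The size cannot be derived from the documents. With a quarter of early stoppers sampled below LLOQ, and the rule applied per arm, the chance of losing an arm's geometric mean is about 10% (n = 20) or 14% (n = 30) if 2% stop early, and about 22% or 31% if 5% do. Quantifiable wash-out values would also lower the averages, without any zero to signal it. The consequence is confined to the descriptive PK output. Primary power and the weight-based choice of target dose are not affected.

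**What to change.** In SAP 2.9, limit the trough summary to samples whose last double-blind dose was taken on the day before sampling. SAP 2.4.1 already derives the last dose date for exposure. List all other samples separately with time since last dose, including those from discontinuation visits and from patients whose drug is interrupted at the visit. Report the number and percentage below LLOQ per arm.

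The geometric-mean rule can stay. Computing the geometric mean on quantifiable values only would bias it upward, most where true troughs are low, so it is not a clear improvement.

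The cost is SAP wording and one programming filter, with no change to study conduct. The downside is a slightly smaller n per arm in the PK table, because completers who missed the previous day's dose would also move to the listing.

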2.10 PD and PK/PD analyses

Not applicable.

2.13 Other Exploratory analyses

Not applicable.

2.14 Interim analysis

Not applicable.

3 Sample size calculation

The study planned to randomize approximately 130 subjects in total, allocated in the ratio of 3:2:2:3:3 to the following Epoch 3 treatment groups:

1. placebo
2. LIK066 2.5 mg qd
3. LIK066 10 mg qd
4. LIK066 25 mg qd
5. LIK066 50 mg qd

This randomization scheme implies that the Epoch 3 treatment for a specific subject is determined simultaneously at randomization visit. The randomization will be stratified by subjects' glycemetic status: T2DM and dysglycemic.

Sample sizes are considered from two viewpoints. One is that this study should be statistically powered to identify the dose-response relationship regarding the effect of LIK066 on weight loss. The other is that this is the first study to enroll Japanese patients, and that the highest dose arms, 25 mg and 50 mg qd arms, and the placebo arm as a control, should include more patients to obtain sufficient information on safety and/or tolerability of LIK066 in Japanese patients. The detail of the first viewpoint will follow.

Table 3-2 summarizes the average power and the lowest power across the candidate dose-response shapes in Figure 2-1, under different scenarios with the assumptions on effect size of body weight loss (percent change from BL) for the dose of maximum effect, and the related standard deviations. In power evaluation, it was also assumed that dose-response is assessed with controlling the overall family-wise type I error at a one-sided significance level of 2.5%.

It was assumed that the effect of losses to follow-up is equivalent to effectively having 10% fewer subjects than randomized, even if the multiple imputation approach used to handle missing values should be able to recover some information for such subjects.

Table 3-1 Power for detecting a significant dose response signal*

Effect size for best dose	Standard deviation	Average power	Minimum power**
3.5%	3%	99.70%	99.52%
3.5%	3.5%	98.11%	97.28%
4.0%	3%	99.97%	99.94%
4.0%	3.5%	99.59%	99.35%

* Assumes 130 subjects in total with effective sample size of 117 subjects due to an effect of missing data equivalent to 10% fewer subjects. Calculations were performed using R Dose Finding package.

** Power for a significant dose-response contrast test across all scenarios mentioned in Section 2.5.2. The quadratic model has the lowest power.

4 Change to protocol specified analyses

Per project-level change, the summary on baseline anti-diabetic medications is changed to be provided by baseline glyceemic status.

Per project-level change, the procedures for modeling dose-response relationship are changed as follows:

- Modeling via the best-fit model is cancelled.
- The model-averaging method is changed.

For efficacy secondary endpoints other than responder in body weight, ANCOVA models are changed depending on their scheduled post-baseline measurement time points

- For endpoints measured *only* at Week 12, the ANCOVA model is changed to the one including treatment and baseline glyceemic status as fixed effect factors, and baseline as a covariate. Such endpoints include HbA1c, FPG, lipid parameters, fat area parameters, urine albumin, urine albumin to creatinine ratio, and log10-transformed hsCRP.
- For other endpoints, baseline status is added to the repeated measure ANCOVA model.

In addition, the models for subgroup analysis are changed to apply the same model by baseline glyceemic status.

- For endpoints measured *only* at Week 12, the ANCOVA model for subgroup analysis is changed to the one including treatment as a fixed effect factor, and baseline as a covariate.
- For other endpoints, the repeated measure ANCOVA model is changed to the one including treatment, visit, and treatment by visit interaction as fixed-effect factors and baseline as a covariate.

5 Appendix

5.1 Imputation rules

5.1.1 Study drug

Any partial dates will be imputed as the earlier day of

- The last day in the month and
- The end day of the corresponding epoch

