1.1.2 Epoch 3 (treatment)

After the run-in Epoch 2, eligible subjects will be randomized in the ratio of 2:2:3:3:3 to one of the following regimes at Visit 201 (randomization):

- 2.5 mg qd LIK066
- 10 mg qd LIK066
- 25 mg qd LIK066
- 50 mg qd LIK066
- Placebo.

At Visit 201, subjects will be randomized simultaneously to one of the five Epoch 3 treatment schedules.

[figure not shown]
At randomization, subjects will be stratified according to their glycemetic status at screening using the following criteria:

- Dysglycemic: no prior clinical diagnosis of T2DM, FPG ≥ 110 mg/dL and/or HbA1c $\geq 5.6\%$, except for HbA1c $\geq 6.5\%$ and FPG ≥ 126 mg/dL at Visit 1 (screening).
- T2DM: prior diagnosis of T2DM, or subjects without prior diagnosis of T2DM with HbA1c $\geq 6.5\%$ and FPG ≥ 126 mg/dL at Visit 1 (screening).

Following randomization, subjects will attend study visits in Epoch 3 (12 weeks) for assessment of efficacy, tolerability and safety parameters. During Epoch 3, subjects will take the study medication.

The doses of antidiabetic and antihypertensive medications should be adjusted in patients who, according to the investigator, could be at a safety risk (e.g. repetitive or severe hypoglycemia, symptoms and signs of volume depletion, etc.).

Figure 1-1 Study design

[figure not shown]
The primary analysis time point is Week 12 (Visit 299). There is no interim analysis planned.

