2.1.1 General definitions

Baseline (Week 0) for the randomized treatment period will be defined as the last measurement before or at the randomization visit.

The first day of administration of randomized study treatment (first dose) is defined as Day 1 for the study. If the date of first administration is missing, then randomization date will be used as Day 1.

All other study days will be labeled relative to Day 1. For event dates on or after Day 1, study day for a particular event date is calculated as [Date of event] – [Date of first dose] + 1. For the dates before Day 1, study day for an event date is calculated as [Date of event] – [Date of first dose]. Duration of an event will be calculated as [Event end date] – [Event start date] + 1. The descriptor "Day 0" will not be used.

The treatment groups presented are:

- LIK066 2.5 mg qd
- LIK066 10 mg qd
- LIK066 25 mg qd
- LIK066 50 mg qd
- Placebo
- Total (if applicable)

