2.4 Treatments (study treatment, rescue medication, concomitant therapies, compliance)

2.4.1 Study treatment / compliance

The duration of double-blind treatment exposure in Epoch 3 will be summarized by treatment group both descriptively in days (mean, standard deviation, minimum, Q1, median, Q3, and maximum) and by duration category in weeks (≤ 2 , >2-4, >4-8, >8-12, and >12) for the SAF.

- Duration of exposure (days) = last dose date of Epoch 3 – first dose date + 1
- Duration of exposure (weeks) = (last dose date of Epoch 3 – first dose date + 1)/7

Overall subject-years on-treatment in Epoch 3 will be reported by each treatment group.

- Overall subject-years on-treatment = sum of duration of treatment exposure (in days) from all subjects / 365.25

The duration of double-blind treatment exposure excluding treatment interruptions in Epoch 3 will also be summarized descriptively and by duration categories as above.

- Duration of exposure excluding treatment interruptions (days) = last dose date of Epoch 3 – first dose date + 1 – number of days of treatment interruption

Number and percentage of subjects with treatment interruption and permanent treatment discontinuations in Epoch 3 will be provided by reason for treatment interruption or discontinuation.

Duration of treatment interruption will also be summarized as appropriate.

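### The study-drug date rule in SAP 5.1.1 does not separate start from end dates, so a partly dated interruption can get a negative length; its overlap with 2.1.1 also leaves a partial first-dose date unsettled

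*SAP*

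**What the plan says.** SAP 5.1.1 gives a single rule for study-drug dates: "Any partial dates will be imputed as the earlier day of" two limits, "The last day in the month and" and "The end day of the corresponding epoch". It does not distinguish start dates from end dates, sets no lower limit, and does not compare an imputed start with a recorded end.

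The neighbouring sections are built differently. SAP 5.1.2 (adverse events) and 5.1.3 (concomitant medication) each have separate start and end rules, and each resets an imputed start that falls after the end date.

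Three other places use these dates:

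- SAP 2.1.1 fixes the time origin: "The first day of administration of randomized study treatment (first dose) is defined as Day 1 for the study". It adds a fallback: "If the date of first administration is missing, then randomization date will be used as Day 1". It does not say whether a date with only the day missing counts as missing.
- SAP 2.1.1 also defines event length: "Duration of an event will be calculated as [Event end date] – [Event start date] + 1".
- SAP 2.4.1 defines exposure excluding interruptions as last dose date minus first dose date plus 1, minus the "number of days of treatment interruption". It also plans a summary of interruption duration itself.

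**The concern.** Taking the earlier of month end and epoch end gives the latest plausible day. For a stop date that is a reasonable convention. For a start date it places the start as late as possible, often after a recorded end.

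For interruptions, no other SAP rule covers a partial start, so 5.1.1 is the only rule to follow. A negative length would enter the interruption summary and be subtracted from exposure, raising the net figure above the gross.

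For the first dose, 5.1.1 and 2.1.1 can both be read as applying, and they give different answers. Day 1 anchors study day (2.1.1), treatment emergence (2.8.1), exposure (2.4.1), the 77-day PPS requirement (2.2), the exposure offset in the diarrhea model (2.8.1.1) and the reference dates for imputing adverse-event and medication starts (5.1.2, 5.1.3). Two programmers could each follow the SAP faithfully and differ on all of these for the same patient.

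**Working it through.** The plan states no figure for a date shift, so there is nothing to reproduce. The check applies the rule as written: imputed date = min(month end, epoch end). Assumptions: the day is missing, month and year are known, and a completer has 84 days of treatment (12 weeks × 7, SAP 1.1.2).

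**Interruption with start day missing and end known.** Length = end − start + 1 (SAP 2.1.1). Take a patient with first dose 3 March and last dose 25 May (84 days).

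- Recorded interruption: April (no day) to 12 April.
- Imputed start: 30 April, because epoch end is later.
- Length: 12 − 30 + 1 = −17 days.
- Exposure excluding interruptions: 84 − (−17) = 101 days, against a total of 84.

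The epoch-end limit does not prevent this. With a true interruption of 3–5 May and epoch end on 20 May, the start becomes 20 May and the length is 5 − 20 + 1 = −14 days.

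To see how often a partial start would give an impossible length, every first-dose date in a 365-day year was combined with every placement of the interruption after Day 1 that ends before the last dosing day:

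| True length (days) | Imputed length negative | Zero or negative | Lowest value |
|---|---|---|---|
| 1 | 92% | 97% | −29 |
| 3 | 86% | 90% | −27 |
| 7 | 73% | 77% | −23 |
| 14 | 50% | 54% | −16 |

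The lowest value occurs when the interruption starts on the 1st of a 31-day month: for true length n it is n − 31 + 1. These are shares of calendar positions given a partial start date. They do not predict how many patients will have one.

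**First-dose date with day missing.** The two readings are:

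- *2.1.1 governs:* Day 1 is the randomization date, with no month-end shift.
- *5.1.1 governs:* Day 1 is month end. For an 84-day epoch the epoch-end limit never binds, so the shift is 0 to 30 days. The mean over a 365-day year is 5,373/365 = 14.7 days, where 5,373 is the sum of m(m − 1)/2 over the twelve month lengths m.

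On the second reading, 3 March becomes 31 March: 28 days late, exposure 84 − 28 = 56 days, and adverse events of 3–30 March precede Day 1. In general:

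- Lowest exposure for a completer: 84 − 30 = 54 days.
- Below the 77 days of SAP 2.2 (shift of 8 or more): (365 − 12 × 8)/365 = 269/365 = 74% of start dates.
- Below the 10 weeks (70 days) of SAP Table 5-3 (shift of 15 or more): (365 − 12 × 15)/365 = 185/365 = 51%.
- If Epoch 3 lasts only 7, 14 or 28 days, the epoch-end limit holds the shift to at most 6, 13 or 27 days.

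**The case against.** The strongest reply is on Day 1. SAP 2.1.1 has a specific rule for the first-dose date, a date without a day can fairly be called missing, and a specific rule normally prevails over a general appendix rule. On that reading 5.1.1 was meant for stop dates and is only loosely worded. This stands as far as it goes. A reader might infer that the plan does move Day 1 by up to 30 days, reclassify on-drug events and drop compliant patients from the PPS. The documents do not support that as a general statement: each of those effects follows only if 5.1.1 is chosen over 2.1.1. Nor does every partial date go to month end, since epoch end applies when it is earlier.

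The second reply concerns frequency. The dose administration record is completed at Visit 201 and every later scheduled visit (protocol Table 6-1), entries pass automatic checks and queries (protocol 8.2, 8.3), and interruptions are allowed only for safety reasons (protocol 5.5.5). Partial dates should therefore be rare. That also stands, and the documents give no count.

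Third, SAP 2.4.1 gives no formula for interruption days, so −17 relies on the general duration formula in 2.1.1. That formula is the only one offered, and any end-minus-start calculation is negative when the start is this far after the end.

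Fourth, the reach is limited. Negative interruption days do not touch the PPS requirement, which SAP 2.2 counts from first to last intake. The PPS itself serves a sensitivity analysis (2.5.4). None of these replies removes the negative length, which nothing else in the SAP prevents.

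**Conclusion.** The point holds at low severity, in two parts of unequal strength.

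- **Interruption dates: established.** Applied as written, 5.1.1 can give a negative interruption length, down to −29 days, and a net exposure above total exposure. This needs a partial start, a complete end, and an end early enough before the imputed start.
- **First-dose date: an unresolved overlap.** The Day 1 shift is 0 to 30 days if 5.1.1 governs and zero if 2.1.1 governs. Effects on study day, treatment emergence, exposure and PPS membership carry the same condition.

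The number of patients affected is unknown and probably small. The primary FAS analysis uses weights recorded at visits and is not directly affected. The point is still worth correcting, because a stated rule that yields impossible values is more than missing detail.

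**What to change.** Amend the SAP as follows:

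1. Limit the rule in 5.1.1 to end dates.
2. State in 2.1.1 that the randomization date also serves as Day 1 when the first-dose date lacks its day and the recorded month is the month of randomization. Otherwise use the later of the randomization date and the first day of the recorded month.
3. Impute a partial interruption start as the later of Day 1 and the first day of the recorded month, never after the recorded end.

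In the worked example the interruption becomes 1–12 April: 12 − 1 + 1 = 12 days, and net exposure is 84 − 12 = 72 days. If the first dose falls on the randomization date or the day after, the Day 1 error becomes 0 to −1 day. The shortest possible interruption becomes +1 day.

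The downside is that interruption length can now be overstated by up to 30 days (a true start on the 31st set to the 1st), but it cannot be negative. The cost is a few lines of SAP text and a small change to the date derivation, with no new data collection.
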